### **9.3. Criteria for Study Termination**

#### **9.3.1. Withdrawal of Subject from Study Treatment**

Subjects will be discontinued from further study treatment in the event of any of the following:

- Unmanageable toxicity per Section 10.5.2.
- Subject's decision/withdrawal of consent (e.g., subject declines further treatment).
- Physician decision that continuation is not in the subject's best interest.
- Termination of the study by the Sponsor.
- Other reasons (e.g., major protocol violation, noncompliance).
- Progressive disease.

If the subject is withdrawn from the study the primary reason must be recorded in the eCRF. If possible, the Investigator should arrange for the EOT visit assessments to be completed.

#### **9.3.2. Early Study Termination**

The Sponsor has the right to close the study at any time, although this should occur only after mutual consultation between the Sponsor and the Investigators. Events that may trigger early study termination include but are not limited to:

- Insufficient efficacy following interim analyses of Groups A and B.
- Significant toxicity finding.
- Insufficient bioavailability to achieve adequate study drug exposure.
- Change in development plans for the study drug.
- Slow recruitment.

A Safety Review Committee (SRC) comprised of the Medical Monitor, PI, and Sponsor representatives will be convened to review safety information on an ongoing basis for safety

surveillance. The SRC is tasked with making a recommendation to continue or stop the trial based on their assessment of available efficacy and safety information.

An initial review of safety data will be conducted by the SRC including all treated patients after the first 15 patients have completed at least one cycle of treatment. Additionally, any treatment-related deaths will be cause for pausing enrollment and initiating SRC review of all safety data.

The SRC will be tasked with making a recommendation to continue or stop the trial based on their assessment of the benefits or risks to patients based on all available safety information including:

- Grade  $\geq 3$  toxicity regardless of relationship to treatment
- Treatment discontinuation due to toxicity
- Dose reduction due to toxicity
- Death regardless of cause

Guidelines for stopping criteria are as follows:

- If a third or more of the patients have treatment-related Grade  $\geq 3$  toxicity, excluding:
  - Grade  $\geq 3$  thrombocytopenia that resolves (Grade  $< 3$ ) within 7 days
  - Grade  $\geq 3$  diarrhea that resolves (to Grade  $< 3$ ) with standard therapy
- $> 10\%$  incidence of colitis, pneumonitis, or severe hepatotoxicity
- $> 10\%$  deaths due to Grade 4 treatment-related toxicity

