**Dose and Mode Of Administration/Dosing Schedule:**

Each cycle will consist of 21 days.

- CUDC-907 60 mg (2 × 30 mg capsules) administered PO 5/2.

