### **10.5. Study Drug Administration**

#### **10.5.1. CUDC-907**

Subjects will receive CUDC-907 60 mg in 21-day cycles.

CUDC-907 will be administered orally at the assigned dose level and schedule, 60 mg on a 5/2 schedule.

All doses of study drug (in clinic and self-administered) will be administered with meals ( $\pm$  30 minutes) at approximately the same time each dosing day, if possible.

Dose and/or schedule intensity of CUDC-907 may be reduced per protocol due to toxicity.

In the absence of significant toxicity, each subject is expected to complete at least 1 cycle (21 days) of study treatment. However, subjects may continue to receive additional 21-day cycles of CUDC-907 treatment until disease progression has been documented or other discontinuation criteria have been met (Section 9.3.1).

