### **15.6. Study Committees**

A Safety Review Committee (SRC) comprised of the Medical Monitor, PI, and Sponsor representatives will be convened to review safety information for ongoing safety surveillance.

The SRC is tasked with making a recommendation to continue or stop the trial based on their assessment of available efficacy and safety information (see Section [9.3.2](#) for SRC stopping criteria).

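### The initial safety review is timed by 15 patients completing a cycle, so it comes somewhat later as Cycle 1 exits rise

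*Combined protocol and SAP*

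**What the plan says.** Protocol Section 9.3.2 (Early Study Termination) gives the timing of the initial SRC review as "after the first 15 patients have completed at least one cycle of treatment". It fixes the data separately: "An initial review of safety data will be conducted by the SRC including all treated patients".

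Other provisions bear on the timing:

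- A second, event-driven trigger is in the same section: "any treatment-related deaths will be cause for pausing enrollment and initiating SRC review of all safety data".
- Sections 9.3.2 and 15.6 describe continuing oversight. In 15.6 the committee "will be convened to review safety information for ongoing safety surveillance". Neither section gives an interval or a patient count.
- The first stopping guideline in 9.3.2 begins "If a third or more of the patients have treatment-related Grade" 3 or higher toxicity, with listed exclusions.
- On cycle length, the synopsis says "Each cycle will consist of 21 days".
- Section 10.5.1 links completing a cycle to tolerability: "In the absence of significant toxicity, each subject is expected to complete at least 1 cycle (21 days) of study treatment".

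No clause counts or replaces, for the purpose of the trigger, a patient who leaves before the end of Cycle 1. No enrollment pause is stated while the 15 completers accumulate.

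**The concern.** A patient who stops during Cycle 1 may carry the very information that an early safety review exists to examine, yet does not bring that review closer. Section 10.5.1 expects completion of the first cycle only when toxicity is not significant, so more early toxicity exits mean a slower count. Exits for progression, withdrawal or an unrelated death slow it in the same way.

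This matters because it is the only safety review with a stated time point. A treatment-related death starts a review, but non-fatal toxicity, which makes up most of what the one-third guideline is about, starts none. Since enrollment continues meanwhile, a later review means more patients treated before the guideline is first formally applied.

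**Working it through.** **Is there a figure to reproduce?** No. The protocol gives no derivation, expected exit rate or operating characteristic for the 15. The check is therefore how the review date moves with the exit rate.

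**Inputs from the documents**
- Completers required: 15 (Section 9.3.2).
- Cycle length: 21 days, or 3 weeks (synopsis).
- Enrollment of about 200 (Section 8.2) and a planned trial period of 2 years (synopsis).

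**Assumptions**
- Accrual is uniform over the whole period: a = 200/104 = 1.92 patients per week. Half this rate is also shown.
- A share d of treated patients leaves before the end of Cycle 1. The documents do not state d, so 10%, 20% and 40% are used as a range.
- The trigger means any 15 patients who have completed a cycle.

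**Formulas**
- Mean number started to obtain 15 completers: N = 15/(1 − d), the negative binomial mean.
- Mean week of review: T = N/a + 3.
- Mean number treated by then: N + 3a, where 3a = 5.8 is the number who start during the final 3 weeks.
- Comparator, a trigger that counts completion or earlier discontinuation: 15 replaces N, so T = 15/1.92 + 3 = 10.8 weeks and 15 + 5.8 = 20.8 patients are treated. This does not depend on d. It is slightly conservative, because the condition could be met sooner if the last of the 15 stops early.

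**Results at 1.92 per week**

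| Cycle 1 exit d | Mean started, N (90th percentile) | Week of review | Delay vs comparator (weeks) | Treated at review |
|---|---|---|---|---|
| Comparator | 15 | 10.80 | – | 20.8 |
| 10% | 16.7 (18) | 11.67 | 0.87 | 22.4 |
| 20% | 18.8 (22) | 12.75 | 1.95 | 24.5 |
| 40% | 25.0 (30) | 16.00 | 5.20 | 30.8 |

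A simulation of 20,000 trials with Poisson accrual agrees with these means to within rounding.

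**Sensitivity to accrual.** The delay is (N − 15)/a. At 0.96 per week it doubles, to about 1.7, 3.9 and 10.4 weeks. The mean number of extra patients treated is N − 15 = 1.7, 3.75 and 10 whatever the accrual rate.

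**Not modeled.** Dose holds under Section 10.5.3.1 could also postpone completion of a cycle, and the protocol does not say how a held cycle is counted. Any such effect would add to the delay.

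**The case against.** The strongest reply is that the delay is small where it is most likely to arise, and that other safeguards cover the interval.

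*Size.* Grade 3 or higher toxicity is not the same as leaving treatment. In Table 2 of Section 10.5.3.3, a first Grade 3 or 4 hematologic event leads to a hold and a reduction, a first Grade 3 non-hematologic event leads to a hold, and hyperglycemia severe enough to need action leads to a hold and a reduction. Section 6.1.3 reports no dose-limiting toxicities at the planned dose and schedule. As an illustration, if 40% had such toxicity and a quarter of them left in Cycle 1, exit for toxicity would be 0.40 × 0.25 = 10%, and the delay under one week at the planned-average accrual. This stands. The 40% row is an upper scenario and should not be read as what happens when the one-third guideline is crossed.

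*Safeguards.* The SRC is to be convened on an ongoing basis. A treatment-related death pauses enrollment and starts a review. A significant toxicity finding is among the listed events that may lead to early termination. Section 12.4.1 requires serious adverse events to reach the sponsor within 24 hours. The Medical Monitor, who sits on the SRC, takes part in decisions on DLT-like events (Section 10.5.3.1). These provisions lower the risk, and they rule out an inference that a reader might draw, that early toxicity goes unseen or is left out of the review. All treated patients are in the data. None of these provisions, however, sets the date of the initial review or guarantees one at a given number of patients when the toxicity is non-fatal.

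*Wording.* A reader might also infer that the 15 are a fixed cohort, so that one early exit among them means the condition can never be met. That reading is strained: a planned review is more sensibly understood to fall due once 15 patients have completed a cycle. The point does not rely on it.

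**Conclusion.** The point holds in a limited form. As written, the timing rule moves the initial review in the unhelpful direction: the more patients leave during Cycle 1, for whatever reason other than a treatment-related death, the later it comes. That direction follows from the wording alone.

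The size rests on assumed exit rates and uniform accrual, neither of which the documents supply. Below 10% exit the effect is negligible in practice. At 20% it is about two weeks and four extra patients, and only at rates near 40% does it reach about five weeks and ten extra patients, in a trial of about 200. Nothing in the protocol is contradictory or miscalculated here, and the documents do not support a claim that non-fatal toxicity goes unmonitored until the 15th completion. The change is worth making because it is cheap and the delay grows in the scenario of most concern.

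**What to change.** In Section 9.3.2, redefine the trigger so that the initial SRC review takes place *when the first 15 treated patients have each either completed Cycle 1 or discontinued earlier for any reason*. Keep the existing clause that puts every treated patient into the data reviewed. The stopping guidelines and the treatment-related death trigger stay as they are.

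The cost is one sentence, with no extra visits, data or staff. The one downside is that fewer of the 15 may have a full cycle of exposure at the review, so the committee's tables should show exposure alongside toxicity.

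The synopsis refers to subjects enrolled on amendment 4, and the documents do not say whether the initial review has already taken place. If it has, the sponsor should record how the 15 were counted.

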## **8.3. Dose and Schedule**

### **8.3.1. Dose and Mode of Administration**

Subjects will receive:

- CUDC-907 60 mg (2  $\times$  30 mg capsules) orally (PO) for 5 days on/2 days off (5/2) (21-day cycles)

CUDC-907 will be administered PO with meals ( $\pm$  30 minutes). CUDC-907 will be administered in the clinic on days of PK blood sampling, biopsy sampling, and on Day 1 of each cycle up to Cycle 13. Beginning on Cycle 14, in-clinic dosing will only be required on Day 1 of even numbered cycles (i.e., Cycles 14, 16, 18, etc.).

If a dose is missed or vomited, the subject will be instructed to skip that dose and report it to the Principal Investigator (PI) as soon as possible. Missed or vomited doses should not be made up.

Subjects must meet retreatment criteria in order to continue receiving study treatment (see [Section 10.5.2](#)).

Treatment delays and dose reductions will be allowed as specified in Section 10.5.3; however subjects who experience a Grade 4 DLT-like event must be discontinued from further study treatment.

For full study treatment details, see Section 10.

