### 10.5.3. Safety Criteria for Adjustment or Stopping CUDC-907

#### 10.5.3.1. Dose Delays and Discontinuation of CUDC-907

In the event that any of the above criteria are not met, study drug dosing must be held until the retreatment criteria are met. Treatment may then resume at the full dose of CUDC-907, as long as none of the criteria in Table 2 are met. Beyond Cycle 1, subjects held for  $> 7$  days may restart treatment after the subject has met the above criteria and following discussion and agreement between the Investigator and the Medical Monitor. Beyond Cycle 2, subjects may have study drug held for up to 7 days between the end of a cycle and initiation of another (e.g., Cycle 2 Day 21 to Cycle 3 Day 1). This hold will be at the discretion of the Investigator and after discussion and agreement between the Investigator and Medical Monitor.

Study treatment should be discontinued in the event of an unacceptable toxicity or treatment hold lasting more than 4 weeks, except in cases of clinical benefit determined by the Investigator with approval by the Sponsor Medical Monitor.

Subjects who experience a DLT-like event will be either discontinued from further study treatment or their dose will be reduced following discussion and agreement between the Investigator and the Sponsor's Medical Monitor. A DLT-like event will be defined as any of the following AEs occurring at any time:

- Non-hematological  $\geq$  Grade 3 AE, other than Grade 3 nausea or Grade 3 vomiting in subjects treated with less than optimal antiemetic therapy.
- An AE resulting in a dose delay of  $\geq$  7 consecutive days (e.g., 6 consecutive missed doses).
- Grade 4 neutropenia  $\geq$  7 days, or  $\geq$  Grade 3 neutropenia with fever  $>$  101.3°F (38.5°C) or  $\geq$  Grade 3 neutropenia with infection.
- Grade 4 thrombocytopenia  $\geq$  7 days, or  $\geq$  Grade 3 thrombocytopenia and significant bleeding.

**NOTE:** A DLT-like event excludes AEs that are clearly and incontrovertibly related to the underlying disease or extraneous factors.

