Non-hematological AEs (excluding hyperglycemia)	Grade 1 or 2 No change in dose 	Grade 3 
 
Hold treatment until resolution to ≤ Grade 1 or baseline
 
If not recovered to ≤ Grade 1 or baseline within 3 weeks, reduce to next lower dose level upon return to ≤ Grade 1 or baseline (as applicable per Table 1).
 
	Grade 4 Discontinue treatment. 
Recurrence of Grade 3 non-hematologic toxicity (excluding hyperglycemia) or inability to reduce dose (based on starting dose) will be grounds for discontinuation of study drug.			

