**Table 2: CUDC-907 Dose Adjustments for Hematologic and Non-Hematologic Toxicities (Continued)**

Toxicity	Management		
Hyperglycemia	Grade 1/2 or Grade 3 (> 250 – 500 mg/dL) asymptomatic No change in dose 	Grade 3 (> 250 – 500 mg/dL) symptomatic or Grade 4 (> 500 mg/dL) Hold treatment until glucose < 250 mg/dL and asymptomatic; Reduce dose to the next lower dose level (as applicable per Table 1 ).	≥ Grade 3 hyperglycemia not improving despite appropriate treatment for 1 week or symptomatic Grade 4 hyperglycemia (> 500 mg/dL) Hold treatment until glucose < 250 mg/dL and asymptomatic; Reduce dose to the next lower dose level (as applicable per Table 1 ) upon return to ≤ Grade 1 or baseline.

Recurrence of Grade 3 or 4 hyperglycemia will be cause for a second dose modification.  If the starting dose does not permit dose modification, then study drug will be discontinued.  Recurrence of Grade 3 or 4 hyperglycemia that does not recover to ≤ Grade 1 or baseline within 3 weeks after second modification (as applicable) will be grounds for discontinuation of study drug.
			

AEs = adverse events; ANC = absolute neutrophil count

 Transient Grade 1 or 2 hyperglycemia should be monitored per Investigator discretion and medical guidelines.

 An exception for ongoing treatment may be made in the case of Investigator-determined clinical benefit with approval from the Medical Monitor.

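### The one-third toxicity guideline in Section 9.3.2 leaves out Grade 4 diarrhea that resolves with standard therapy, an event for which the protocol stops treatment

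*Combined protocol and SAP*

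**What the plan says.** Section 9.3.2 (Early Study Termination) sets the first SRC safety review as "including all treated patients after the first 15 patients have completed at least one cycle of treatment". Its first stopping guideline is met when a third or more of patients have treatment-related toxicity of Grade 3 or higher, with two exclusions. One is thrombocytopenia that resolves within 7 days. The other is Grade 3 or higher "diarrhea that resolves (to Grade" below 3) with standard therapy. The diarrhea exclusion carries no upper grade.

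The same section lists what the SRC reviews: all Grade 3 or higher toxicity whatever its cause, "Treatment discontinuation due to toxicity", dose reductions for toxicity, and deaths. Separate guidelines of more than 10% cover colitis, pneumonitis or severe hepatotoxicity, and deaths due to Grade 4 treatment-related toxicity.

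For the individual subject the rules are stricter:

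- Section 8.3.1: "subjects who experience a Grade 4 DLT-like event must be discontinued from further study treatment".
- Section 10.5.3.1: a DLT-like event includes any non-hematological adverse event of Grade 3 or higher, "other than Grade 3 nausea or Grade 3 vomiting in subjects treated with less than optimal antiemetic therapy". Diarrhea has no such exception.
- Table 2 (Section 10.5.3.3): a Grade 4 non-hematological event means stopping treatment. Footnote 2 softens this: "An exception for ongoing treatment may be made in the case of Investigator-determined clinical benefit", with Medical Monitor approval.

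**The concern.** An exclusion for diarrhea that supportive care controls is reasonable for this drug. Its wording, however, starts at Grade 3 and has no ceiling, so it also takes in Grade 4. A subject can then be removed from treatment for Grade 4 diarrhea under Section 8.3.1 and Table 2 and still add nothing to the toxicity count, because the diarrhea came down on loperamide and fluids.

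At stake is whether the count reflects treatment-ending toxicity. The one-third guideline is the main numeric check on severe, non-fatal diarrhea that is not called colitis, and no numeric guideline is tied to discontinuations. Near the threshold a single subject decides the matter. When such a subject is left out, action depends on the committee's general judgment rather than on the pre-set count.

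**Working it through.** **The text.** Take a subject whose only treatment-related event of Grade 3 or higher is Grade 4 diarrhea that falls to Grade 2 on antidiarrheals and rehydration.

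| Rule | Result for this subject |
|---|---|
| 8.3.1, Grade 4 DLT-like event | Discontinue |
| Table 2, Grade 4 non-hematological event | Discontinue, unless footnote 2 is applied |
| 10.5.3.1, supportive-care exception | Not available: nausea or vomiting only, Grade 3 only |
| 9.3.2, one-third guideline | Not counted |

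**One-subject example, placed at the threshold on purpose.** There are 15 treated. Four have other counted events and one has the event above.

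- As worded: 4/15 = 27%, guideline not met.
- If the event is counted: 5/15 = 33%, guideline met.

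**Size.** The plan states no operating characteristics for this guideline, so there is no figure to reproduce. The documents also give no rate of Grade 3 or Grade 4 diarrhea. The rates below are therefore assumptions.

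Inputs:

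- n = 15 at the first review (Section 9.3.2). Because all treated patients are included, n may be larger, and 20 is shown as well.
- Threshold r = n/3 rounded up: 5 of 15, or 7 of 20.
- b = proportion with other counted events, assumed 10% or 20%.
- q = proportion with newly counted diarrhea, assumed 2% or 5%, independent of b.

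Formulas: as worded, p = b. With the diarrhea counted, p = 1 − (1 − b)(1 − q). P(guideline met) = P(X ≥ r) with X ~ Binomial(n, p).

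For n = 15 and b = 0.20, P(X ≥ 5) = 1 − P(X ≤ 4) = 1 − 0.836 = 0.164. With q = 0.05, p = 1 − 0.80 × 0.95 = 0.24 and P(X ≥ 5) = 0.281.

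| n (needed) | b | As worded | q = 2% | q = 5% |
|---|---|---|---|---|
| 15 (5) | 20% | 0.164 | 0.208 | 0.281 |
| 15 (5) | 10% | 0.013 | 0.025 | 0.055 |
| 20 (7) | 20% | 0.087 | 0.121 | 0.184 |
| 20 (7) | 10% | 0.002 | 0.006 | 0.018 |

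**Overlap.** Independence is not the only possibility.

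- If the two kinds of event never occur in the same subject, p = b + q. For n = 15, b = 20%, q = 5% this is 0.25, and P = 0.314.
- If half of the newly counted subjects already have another counted event, p = 0.20 + 0.05/2 = 0.225, and P = 0.234.
- If all of them do, p = b and nothing changes from 0.164.

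Positive overlap is plausible. Section 10.6.1 names dehydration and electrolyte imbalance as consequences of diarrhea, and either one counts if recorded as a treatment-related event of Grade 3 or higher.

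**Where the rate may lie.** Section 6.1.3 reports no DLTs at 60 mg on the 5/2 schedule. Section 6.3.1 places the 4 diarrhea and hyperglycemia DLTs (3 subjects) at the highest doses on other schedules. It also lists diarrhea among drug-related Grade 3 or 4 events seen in 2 or more subjects, without a rate or dose. This points toward the lower values of q.

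**The case against.** The strongest reply is that little is lost. The SRC reviews every Grade 3 or higher event and every discontinuation or dose reduction for toxicity, and it decides on all available safety information. The numeric criteria are guidelines, and a significant toxicity finding is a separate ground for early termination. Diarrhea that does not resolve with standard therapy is counted, and colitis has its own guideline, which 2 of 15 (13%) would exceed. All of this stands, and it sets the weight of the point.

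It can also be said that dosing rules for one subject and a stopping guideline for the trial serve different purposes and need not match. That is fair as a general principle. It does not explain why an exclusion for manageable diarrhea should reach Grade 4, when the protocol's other supportive-care exception stops at Grade 3.

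Two stronger readings are tempting, and the documents do not support them:

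- **That these events escape the committee.** They do not. They are missing from one advisory count only.
- **That the exclusion is equally at fault for Grade 3 diarrhea that ends treatment.** Section 10.6.1 describes supportive care as antidiarrheals, rehydration and electrolyte repletion; stopping the drug is not listed. Diarrhea that settles only after the drug is stopped is therefore most naturally counted already. Grade 3 is also not treatment-ending by default: Table 2 holds the drug until recovery, and Section 10.5.3.1 offers dose reduction as an alternative. A recurrent Grade 3 episode can be grounds for stopping and yet resolve on therapy. But a count tied to discontinuation would depend on physician or subject choice (Section 9.3.1) and on agreement with the Medical Monitor (Section 10.5.3.1), who sits on the SRC.

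**Conclusion.** The point holds for Grade 4 diarrhea. As worded, the one-third guideline excludes Grade 4 diarrhea that resolves to below Grade 3 with standard therapy, although the protocol discontinues that subject unless the clinical-benefit exception is used.

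The effect is modest. Under independence, with 15 treated and assumed rates of 2% to 5%, the chance of meeting the guideline rises by about 4 to 12 percentage points when other counted events are at 20% (0.208 − 0.164 = 0.044; 0.281 − 0.164 = 0.117). At 10% it rises by about 1 to 4 points (0.025 − 0.013 = 0.012; 0.055 − 0.013 = 0.042). The increase shrinks toward zero as more of these subjects have other counted events. Since the committee sees the events anyway, the severity is low, and the case for change is that the change is cheap.

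**What to change.** In Section 9.3.2, limit the second exclusion to Grade 3. Suggested wording: *Grade 3 diarrhea that resolves to Grade < 3 with standard therapy (Section 10.6.1).*

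Optionally, add a sentence stating that diarrhea which settles only after permanent discontinuation of CUDC-907 is not resolution with standard therapy and is counted. This settles the natural reading in writing without making the count depend on the decision to discontinue.

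The cost is one bullet. The main change needs only the severity grade, which Section 12.2 already requires for every adverse event. The downside is that the guideline is met slightly more often, by the amounts shown, and so the SRC would more often have to consider a recommendation to stop.
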